#### **Advanced Solid Malignancies**

The Tumor, Nodes, Metastasis (TNM) staging system developed by the American Joint Committee on Cancer (AJCC) will be used to record the subject's clinical stage. Disease response will be assessed using the RECIST 1.1 criteria.

For cohorts that have at least 5 subjects at the recommended Part B dose of 75 mg BID, the following endpoints will be used to determine the response to treatment with ASN002 in subjects with solid tumors:

- Objective Response Rate
- Duration of Response

- TTP
- PFS
- PFS rate at week 24

For cohorts with less than 5 subjects at the recommended Part B dose of 75 mg BID, efficacy will be summarized in a descriptive manner for those subjects who have at least stable disease per protocol criteria.

### **Myelofibrosis**

The International Working Group-Myeloproliferative Neoplasms Research and Treatment (IWG-MRT) and European LeukemiaNet (ELN) response criteria will be used to evaluate the response to treatment with ASN002. If less than 5 subjects were enrolled at the recommended Part B dose of 75 mg BID, efficacy will be summarized in a descriptive manner for those subjects who have at least stable disease per protocol criteria.

The following endpoints will be used to determine the response to treatment with ASN002 in subjects with MF:

- Splenic response rate at week 24
- Clinical improvement rate at week 24
- Symptom response evaluated using the Myeloproliferative Neoplasm Symptom Assessment Form (MPN-SAF) tool
- rate of RBC transfusion through week 24

### **CLL**

The response in patients with CLL will be evaluated according to the criteria of the International Workshop on Chronic Lymphocytic Leukemia with the exception that lymphocytosis will not be the sole criterion for disease progression. For patients with persistent lymphocytosis, a partial response in all other measures will be defined as a partial response with lymphocytosis.

If less than 5 subjects were enrolled at the recommended Part B dose of 75 mg BID, efficacy will be summarized in a descriptive manner for those subjects who have at least stable disease per protocol criteria.

The following endpoints will be used to determine the response to treatment with ASN002 in subjects with CLL:

- Objective Response Rate
- Duration of Response
- TTP
- PFS
- PFS rate at week 24

### **2.3.1.2 Secondary Efficacy Variables**

- Eastern Cooperative Oncology Group (ECOG) performance status – ECOG performance status will be assessed in accordance with the schedule of assessments ([Section 3.2](#)). Change from baseline in ECOG performance status will be evaluated for each post-baseline assessment.

### **2.3.1.3 Exploratory Efficacy Variables**

The exploratory pharmacodynamics variables for efficacy are:

- Inhibition of phosphorylation of S6, STAT3, SYK 525/526, and ERK.
- Inhibition of the basal B-cell surface activation markers, CD69 and CD88.
- Change from baseline in JAK (V617F) in ML patients.
- Change from baseline in BCL and chromosome 17p in CLL patients.
- Reduction of CRP,  $\beta$ 2-microglobulin, and IL-10.
- Change from baseline in a panel of markers of inflammation (see Appendix C of the Study Protocol for the panel of markers).

## **2.3.2 Safety Evaluations**

The primary objective of part A of the study is to evaluate the safety and tolerability of ASN002 including DLTs and to determine the MTD. This will be accomplished by evaluation of the safety and occurrence of DLTs at each dose level.

All adverse events (AEs), unless they have been determined to be not related to study drug, will be taken into consideration in determining a DLT. NCI CTCAE version 4.03 will be used to grade AEs. A DLT is defined as follows:

#### **Non-hematologic DLT**

Any grade  $\geq 3$  AE, with the following exceptions: symptomatic adverse events such as nausea, vomiting and diarrhea will not be considered dose limiting if they can be reduced to less than grade 3 within 72 hours with standard supportive measures such as antiemetics and antidiarrheals.

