#### **Non-hematologic DLT is defined as:**

Any Grade  $\geq 3$  AE, with the following exceptions

- Symptomatic adverse events such as nausea, vomiting and diarrhea will not be considered dose limiting if they can be reduced to less than grade 3 within 72 hours with standard supportive measures such as antiemetics and antidiarrheals.
- Asymptomatic Grade 3 electrolyte abnormalities which can be corrected by optimal supplementation.

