## 15 STATISTICAL CONSIDERATIONS AND METHODS

This section outlines the statistical methodology and principles which will be used for data analysis in this study. A separate statistical analysis plan (SAP) will further describe the details regarding statistical methods and will govern the analysis. Where differences occur between the protocol and the SAP, the SAP will take priority.

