#### **Hematologic DLT**

- A grade  $\geq 4$  neutropenia or thrombocytopenia that lasts more than 7 days after the last dose of study drug;
- Febrile neutropenia;
- A grade  $\geq 3$  thrombocytopenia in the presence of bleeding.

If one of the first 3 patients treated at a given dose level develops a DLT, up to 3 additional patients are to be treated at that dose level. If at least 2 patients treated at a given dose level develop DLT, dose escalation is to be stopped, and the penultimate dose level will be considered the MTD.

The MTD is defined as a dose level immediately below that at which  $\geq 2$  of 6 subjects experience a DLT. Subjects considered to be evaluable for the MTD determination are the subjects who have received the study drug for 28 days or who have discontinued the study drug earlier than 28 days because of a DLT.

The safety evaluations used to define tolerability and determine DLTs will include the following:

- Adverse events (AEs), monitored from the time the subject signs the consent form until 30 days after the last dose of ASN002;
- Prior, concomitant, and post medication use;
- Extent of exposure to study drug;
- Study drug compliance;
- Clinical laboratory tests (hematology, lipid panel, liver function, comprehensive metabolic panel, urinalysis, pregnancy [if applicable]);
- Vital signs;
- 12-lead Electrocardiogram (ECG);
- Physical examination.

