#### **10.1 Adverse Events**

Treatment emergent adverse events (TEAE) will be classified into a standardized terminology using the Medical Dictionary for Regulatory Activities (MedDRA, version 17.0 or higher) system organ classifications and preferred terms. All summaries of the incidence of treatment-emergent adverse events will be provided using the Safety Population by treatment cohort and overall. Although a preferred term or system organ class may be reported more than once for a subject, each subject will only be counted once in the incidence count for that preferred term or system organ class. Summaries of the following types will be provided:

- Summary of treatment-emergent adverse events;
- Summary of treatment-emergent adverse events by MedDRA system organ class and MedDRA preferred term;
- Summary of treatment-emergent adverse events by MedDRA system organ class, MedDRA preferred term, relationship to study drug, and intensity;

- Summary of serious treatment-emergent adverse events leading to discontinuation from the study by MedDRA preferred term, sorted alphabetically by system organ class and preferred term;
- Summary of treatment-emergent adverse events leading to discontinuation from the study by MedDRA preferred term, sorted alphabetically by system organ class and preferred term.

These summaries will present the number and percentage of subjects reporting an adverse event for each classification level. The denominators for calculating the percentages will be based on the number of exposed subjects in the Safety population (i.e., study drug was administered) in the treatment cohort summarized.

Listing of subject dropouts due to AEs prior to post-dose tumor assessment will be generated. All adverse events, serious adverse events and deaths, and adverse events leading to discontinuation from the study will also be provided in data listings by subject.

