# **11 OTHER ANALYSES**

## **11.1 Dose Escalation Safety Analyses**

The study will include multiple safety analyses for the dose escalation component (Part A). Each treatment cohort is viewed as a separate safety analysis, insofar as the safety review committee will decide whether the dose escalation will continue to the next planned (or intermediate) dose level, if additional subjects will be added to the current dose level, or if the dose escalation will be stopped. The safety review committee can also terminate the study due to safety concerns. Each review will be conducted with the latest available data.

---

A data listing of dose-limiting toxicities (DLTs) for Part A will be presented by subject.

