### **14 SUMMARY OF CHANGES FROM THE PROTOCOL**

No changes from the protocol were made in this analysis plan.

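### The SAP drops the protocol's electrolyte exception from the DLT definition and plans no table of all serious events by dose, yet declares no changes

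*SAP*

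**What the plan says.** **DLT definition.** Protocol 8.5.3, and the synopsis in the same terms, counts any non-hematologic event of Grade 3 or above as a DLT, with two exceptions. The first covers symptoms such as nausea, vomiting and diarrhea that supportive care controls. The second reads: "Asymptomatic Grade 3 electrolyte abnormalities which can be corrected by optimal supplementation". SAP 2.3.2 also speaks of exceptions in the plural, but lists only the first: such symptoms "will not be considered dose limiting if they can be reduced to less than grade 3 within 72 hours with standard supportive measures". The electrolyte exception does not appear in the SAP.

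**Use of DLTs.** On the Part A primary objective, SAP 2.3.2 states: "This will be accomplished by evaluation of the safety and occurrence of DLTs at each dose level". The same section restates the MTD rule under its own definition: "The MTD is defined as a dose level immediately below that at which" at least 2 of 6 subjects have a DLT. The output named in SAP 11.1 is a listing: "A data listing of dose-limiting toxicities (DLTs) for Part A will be presented by subject".

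**Serious events.** The protocol synopsis (Safety Analyses) bases the safety assessment on the incidence, at each dose level, of AEs, of AEs resulting in discontinuation and of SAEs, and says that the last two are summarized separately. Protocol 15.5.4 places the SAE summary by preferred term and dose level. SAP 10.1 names five summaries. The only one about serious events is: "Summary of serious treatment-emergent adverse events leading to discontinuation from the study by MedDRA preferred term".

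**Precedence.** Protocol section 15: "Where differences occur between the protocol and the SAP, the SAP will take priority". SAP 14: "No changes from the protocol were made in this analysis plan".

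**The concern.** Each mismatch could be a drafting slip, but the documents offer no way to resolve them in the protocol's favor. A programmer who follows the stated order of precedence applies the SAP, and SAP 14 gives no hint that anything differs.

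The DLT definition serves a primary objective. The SAP's version is broader, so it can only add DLTs. If a subject has a correctable, asymptomatic Grade 3 electrolyte abnormality in Cycle 1, the reported DLT listing, and any MTD restated in the report under the SAP's definition, could contradict what the safety review committee decided under the protocol. The definition is still in use: dose finding continues in solid tumors (protocol 6.4.4), up to 24 more subjects may enter Part A (SAP 4), and the main electrolytes are in the laboratory panel (protocol Table 10), so such events would be detected.

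Safety is a primary objective in both parts. Without a table of all serious events, their incidence by dose has to be worked out by hand from listings.

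**Working it through.** This is mainly a comparison of texts. The plan states no figure to reproduce on this point.

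**1. Non-hematologic DLT, Grade 3 or above**

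| Exception | Protocol synopsis and 8.5.3 | SAP 2.3.2 |
|---|---|---|
| Nausea, vomiting, diarrhea and the like, controlled within 72 hours | Yes | Yes |
| Asymptomatic Grade 3 electrolyte abnormality, correctable | Yes | Absent |

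Every protocol DLT is also a SAP DLT, and the reverse is not true. The SAP count is therefore never below the protocol count.

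**2. What one such event does to a cohort.** Take a cohort of 6 with one protocol DLT, plus one other subject whose only qualifying event is of the excepted electrolyte kind.
- Protocol: 1/6 = 16.7%, below the threshold.
- SAP: 2/6 = 33.3%, which meets the rule of at least 2 of 6.

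The documents give no rate for these events. Protocol 6.3 lists no electrolyte term among the individual events seen in more than 10% of the first 27 subjects.

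**3. Illustration under assumed rates.** Let p be the per-subject probability of a protocol DLT and q that of an excepted electrolyte event, assumed independent. Under the SAP wording the DLT probability is p' = 1 − (1 − p)(1 − q). For a 3+3 cohort run and judged wholly under one definition, the probability of reaching the stopping threshold is

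P = 1 − [(1 − p')³ + 3p'(1 − p')² × (1 − p')³].

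With p = 0.10 and q = 0: 1 − [0.7290 + 0.2430 × 0.7290] = 9.4%. With q = 0.05, p' = 0.145 and P = 17.6%.

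| p | q = 0 (protocol) | q = 0.02 | q = 0.05 | q = 0.10 |
|---|---|---|---|---|
| 0.05 | 2.7% | 4.8% | 9.0% | 17.6% |
| 0.10 | 9.4% | 12.5% | 17.6% | 27.0% |
| 0.20 | 29.1% | 32.6% | 37.9% | 46.4% |

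Both p and q are assumptions, and the committee does not escalate under the SAP. The table shows only how sensitive a 3+3 rule is to a wider definition, and the verdict does not rest on it.

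**4. Serious events**

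| Summary | Protocol synopsis and 15.5.4 | SAP 10.1 |
|---|---|---|
| All SAEs, by dose level | Yes | No named table |
| AEs leading to discontinuation | Yes, separate | Yes (fifth item) |
| Serious TEAEs leading to discontinuation | Not asked for as such | Yes (fourth item) |

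The fourth SAP item is a subset of the fifth, so it brings in no serious event that the fifth does not already hold. Read alone, the sentence in protocol 15.5.4 could be taken to mean SAEs that led to discontinuation. The synopsis rules that out, because it names SAE incidence as an item of its own and asks for separate summaries.

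**5. How common SAEs are.** Protocol 6.3, cut-off 09 February 2017: 11 of 27 subjects, 11/27 = 40.7%, exact (Clopper-Pearson) 95% CI 22.4% to 61.2%. None was considered related to study drug. The documents do not say how many of these SAEs led to discontinuation from the study, so a table like the fourth SAP item could miss anywhere from 0 to 11 of these subjects.

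**The case against.** The best case on the other side is that these are slips with little consequence. The priority clause sits in the protocol's statistical section and concerns the analysis. DLTs are a conduct rule applied by the safety review committee under protocol 8.5, and the SAP introduction refers readers to the protocol for study conduct. A plural followed by one item, together with a statement of no changes, looks like a lost bullet. The SAP plans no table of DLT rates and no re-derivation of the MTD, only a listing. The Part B dose was agreed on 18 May 2017 on grounds that mention no electrolyte event (protocol 6.4.3), and the error is in the cautious direction.

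On SAEs, treatment-emergent serious events are already counted in the general TEAE tables, every SAE is listed by subject, listings are sorted by part and dosing cohort (SAP 6.6), and Part A escalation cohorts are generally 3 to 6 subjects. The first item in SAP 10.1 might be an overview with a row for SAEs. The 41% is a rate of SAEs, not a measure of what is lost.

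Most of this stands as a limit on weight. Escalation is unaffected, the omission is probably accidental, and 41% shows only that SAEs are frequent enough to deserve a table. It does not remove the mismatch. The DLT listing is itself an analysis output and would be produced under the wrong definition. General TEAE tables do not separate serious from non-serious events, and the SAP does not say that its first summary contains an SAE row.

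**Conclusion.** The concern holds on both counts. These are stated rules that contradict the protocol, not detail left open. As written, the SAP would report as DLTs events that the protocol excludes, and would give no named table of all serious events by dose, while stating that nothing changed.

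For DLTs the size is conditional: a single excepted event can shift a cohort from 1 of 6 to 2 of 6, but only if one occurs, and no probability can be given. The effect falls on the reported DLT listing and on any MTD restated in the report, not on the committee's escalation decisions. For SAEs, what is lost is tabulated incidence by dose, in a study where 11 of 27 subjects (41%) had an SAE by the cut-off. The underlying data remain in listings and within the general TEAE counts. The correction should be made before database lock.

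**What to change.** - In SAP 2.3.2, restore the exception for asymptomatic, correctable Grade 3 electrolyte abnormalities so that the definition matches protocol 8.5.3. Merely recording the difference in SAP 14 would not be enough, because the report would still use a definition other than the one the committee applied.
- In SAP 10.1, replace the fourth summary with one of all serious treatment-emergent adverse events by system organ class, preferred term and dose cohort. Keep the fifth summary, of all treatment-emergent events leading to discontinuation, as a separate table.
- With both corrected, the statement in SAP 14 becomes accurate on these two points.

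The cost is one restored clause and one standard table. No new data are needed.

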#### **Hematologic DLT**

- A grade  $\geq 4$  neutropenia or thrombocytopenia that lasts more than 7 days after the last dose of study drug;
- Febrile neutropenia;
- A grade  $\geq 3$  thrombocytopenia in the presence of bleeding.

If one of the first 3 patients treated at a given dose level develops a DLT, up to 3 additional patients are to be treated at that dose level. If at least 2 patients treated at a given dose level develop DLT, dose escalation is to be stopped, and the penultimate dose level will be considered the MTD.

The MTD is defined as a dose level immediately below that at which  $\geq 2$  of 6 subjects experience a DLT. Subjects considered to be evaluable for the MTD determination are the subjects who have received the study drug for 28 days or who have discontinued the study drug earlier than 28 days because of a DLT.

The safety evaluations used to define tolerability and determine DLTs will include the following:

- Adverse events (AEs), monitored from the time the subject signs the consent form until 30 days after the last dose of ASN002;
- Prior, concomitant, and post medication use;
- Extent of exposure to study drug;
- Study drug compliance;
- Clinical laboratory tests (hematology, lipid panel, liver function, comprehensive metabolic panel, urinalysis, pregnancy [if applicable]);
- Vital signs;
- 12-lead Electrocardiogram (ECG);
- Physical examination.

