#### **8.4.1 Missed or Vomited Doses**

Should the subject forget to take the study drug, s/he should take the study drug as soon as s/he remembers up to 2 hours after the planned dosing time. Thereafter, the forgotten dose should not be taken. Vomited doses should not be retaken.

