#### **8.5.2 Dose Escalation Criteria**

Dose escalation will continue until the MTD, a plateau of ASN002 plasma concentration has been identified, or until the planned highest dose level is reached (refer to section **8.3.1**).

Initially, 3 subjects will be treated at the same dose level. There will be at least a 24-hour interval between the administrations of the first dose of the study drug for each subject.

After a minimum of 3 subjects in each cohort have completed cycle 1 of treatment and the safety review has been performed, 3 new subjects can be enrolled at the next higher dose level, in the absence of DLT. No intra-subject dose escalation is permitted during the dose escalation phase.

If 1 of the first 3 subjects experiences a DLT, an additional 3 subjects will be enrolled at the same dose level. The dose escalation will be stopped if 2 or more subjects among a cohort of 3 or 6 subjects experience a DLT. Three additional subjects will be entered to the previous lower dose level cohort, if only 3 subjects were treated in that cohort.

The MTD is defined as a dose level immediately below that at which  $\geq 2$  of 6 subjects experience a DLT. Subjects considered to be evaluable for the MTD determination are the subjects who have received the study drug for 28 days or who have discontinued the study drug earlier than 28 days because of a DLT.

Dose escalation can also be stopped based on the PK data if a plateau in ASN002 plasma concentration versus the dose curve is observed prior to reaching the MTD. Subsequent development decisions regarding the therapeutic doses of ASN002 for future studies will be considered in the evaluation of PK data.

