### 9.3.1 Replacement Procedures

During Part A, a subject who prematurely discontinues from the study before completing 28 days of the dose escalation component for reasons other than DLT, or has demonstrated significant non-compliance with ASN002 dosing, may be replaced at the discretion of the sponsor. Subjects participating in Parts B who discontinue from the study due to non-compliance or protocol violations may be replaced at the discretion of the Sponsor.

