## **10.7 Treatment Compliance**

Study drug compliance will be calculated weekly during Cycle 1. In subsequent cycles, compliance will be calculated on Day 1 prior to receiving additional ASN002. Subjects taking too much or too little study drug should be re-educated on the proper use of study drug. Repeated non-compliance (less than 80% or greater than 100%) should be evaluated by the investigator for the need to withdraw the subject.

Compliance can be assessed using the following formula:

(Number of tablets taken/number of tablets required per protocol) \* 100 = % compliance

Accidental or intentional overdoses should be reported to the sponsor/designee promptly (refer to Section 12.6.1).

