f Refer to the Schedule of Assessments Table for Day 1, and Day 15. Day 3 and Day 16 apply to QD dosing cohorts only.

g Laboratory assessments may be drawn up to 72 hours in advance of the scheduled visit for patient convenience. Refer to Error! Reference source not found. for a complete list of required safety laboratory assessments. Labs need not be repeated on day 1 cycle 1 if baseline data were obtained within the preceding 72 hours.

h Subjects will be evaluated based on malignancy-specific requirements. Evaluations may be completed up to one week prior to the nominal visit.

2014 Lugano Classification (every 12 weeks  $\pm$  1 week) or

RECIST 1.1 for advanced solid tumors every 8 weeks for the first 24 weeks, and every 12 weeks thereafter after the initiation of treatment with ASN002.

i In the QD dosing cohorts, the Day 2 dose should be omitted. All other assessments should be performed.

j PK samples are to be drawn as trough samples prior to study drug administration.

k Cycle 2, Day 1 only, prior to dose administration.

l 30-day follow up for Adverse Events may be conducted as a telephone contact.

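### The MTD-evaluable definition sets no minimum share of planned doses, so a DLT-free Part A subject who completes Cycle 1 under-dosed counts as full evidence of tolerability

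*SAP*

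**What the plan says.** Protocol 8.5.2 and SAP 2.3.2 use the same definition, which in the SAP reads: "Subjects considered to be evaluable for the MTD determination are the subjects who have received the study drug for 28 days". Stopping sooner on account of a DLT also qualifies. Neither text mentions a number or percentage of doses.

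The decision rule is a 3+3. On expansion, Protocol 8.5.2 says: "If 1 of the first 3 subjects experiences a DLT, an additional 3 subjects will be enrolled at the same dose level". On stopping: "The dose escalation will be stopped if 2 or more subjects among a cohort of 3 or 6 subjects experience a DLT".

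Other provisions bear on under-dosing, but none is tied to this definition:

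- Protocol 9.3.1: a Part A subject who "has demonstrated significant non-compliance with ASN002 dosing, may be replaced at the discretion of the sponsor". Significant is not defined.
- Protocol 10.7: compliance is calculated weekly in Cycle 1 from tablets taken over tablets required. "Repeated non-compliance (less than 80% or greater than 100%) should be evaluated by the investigator" for possible withdrawal.
- SAP 8.3: repeated compliance below 80% may be a major protocol deviation. Under SAP 5.3 that affects the Per-Protocol efficacy population.
- Protocol 8.1 and SAP 3.1: subjects unable to complete Cycle 1 for reasons other than a DLT are to be replaced.
- Protocol 8.4.1: a dose remembered more than 2 hours late is skipped. "Vomited doses should not be retaken".

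**The concern.** Evaluability measures calendar time, while the question put to each cohort is whether the assigned dose is tolerated. Someone who stays on study drug to Day 28 but takes, say, half the doses and has no DLT satisfies the definition and counts the same as someone who took every dose.

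This is foreseeable. Much Part A dosing is at home, and late or vomited doses are not made up. Vomiting brought below Grade 3 within 72 hours is not a DLT (Protocol 8.5.3, SAP 2.3.2), so a subject can lose doses to it and remain DLT-free. Protocol 6.3 reports vomiting of any cause in 4 of 27 patients (15%), although it does not say whether doses were lost.

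Each level is judged on three to six subjects, so one misclassified subject matters. The MTD is Part A's primary objective, and dose finding continues: Protocol 6.4.4 keeps it open in solid tumors, and Protocol 8.2 provides for 24 further subjects.

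**Working it through.** The documents give no target DLT rate or operating characteristic for the 3+3 rule, so there is no stated figure to reproduce.

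**Inputs.** The rule is from Protocol 8.5.2. A level is taken as cleared with 0 DLTs in the first three, or 1 in the first three and 0 in the next three; two or more stop escalation. The DLT rates are assumptions: p for a fully dosed subject, q for an under-dosed one.

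**All fully dosed, p = 0.33.**

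- P(0 of 3) = 0.67³ = 0.301
- P(1 of 3) = 3 × 0.33 × 0.67² = 0.444
- P(cleared) = 0.301 + 0.444 × 0.301 = 0.434

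**One of the first three under-dosed, the other subjects at p = 0.33.**

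- P(0 of 3) = (1 − q) × 0.67² = 0.449(1 − q)
- P(1 of 3) = q × 0.67² + (1 − q) × 2 × 0.33 × 0.67 = 0.449q + 0.442(1 − q)
- q = 0.10: 0.404 + 0.443 × 0.301 = 0.537
- q = 0.20: 0.359 + 0.444 × 0.301 = 0.493

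Two under-dosed among the first three would give 0.659 (q = 0.10) or 0.557 (q = 0.20). That is an extreme case, given weekly compliance checks.

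**Sensitivity to the assumed rates.** P(cleared), with the under-dosed subject at half or none of the full-dose risk:

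| p at full dosing | All fully dosed | One of first three, half risk | One of first three, zero risk |
|---|---|---|---|
| 0.20 | 0.71 | 0.76 | 0.80 |
| 0.33 | 0.43 | 0.51 | 0.58 |
| 0.40 | 0.31 | 0.39 | 0.46 |
| 0.50 | 0.17 | 0.24 | 0.31 |
| 0.60 | 0.08 | 0.14 | 0.19 |

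The chance of clearing rises in every row. The direction needs only that under-dosing lowers the DLT risk; the size depends on how far.

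**Planned doses in Cycle 1.** A dose share needs a denominator, and the texts disagree for the BID cohorts.

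- BID, repeat dosing from Day 2 (Protocol 8.4): 1 + 27 × 2 = 55 doses; 80% is 44.
- BID, repeat dosing from Day 3 (Protocol 8.1, SAP 3.1): 1 + 26 × 2 = 53 doses; 80% is 42.4, so at least 43.
- QD, Day 2 omitted: 27 doses; 80% is 21.6, so at least 22.

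**The case against.** The strongest reply is that the plan already limits this problem. Compliance is checked weekly in Cycle 1, subjects are re-educated, and repeated compliance below 80% prompts a withdrawal review. A subject withdrawn on that ground has not completed Cycle 1 and is to be replaced. Section 9.3.1 permits replacement of a non-compliant subject who has not stopped, and replacement would have little purpose in a 3+3 if that subject still counted. SAP 2.3.2 lists exposure and compliance among the evaluations used to define tolerability and determine DLTs. Part A also has site-administered doses and trough PK samples.

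Most of this stands, and it makes gross under-dosing unlikely to go unnoticed. It does not supply a rule: replacement under 9.3.1 is optional, has no threshold and leaves the evaluable set unchanged, and the 80% limits lead to withdrawal review or the efficacy population. The data listed for safety review in Protocol 8.5.1 do not name compliance.

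Three stronger readings are tempting but unsupported.

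- A reader might infer that no QD subject is evaluable, because "In the QD dosing cohorts, the Day 2 dose should be omitted" leaves at most 27 dosing days. That is strained: Protocol 10.2.9 treats Day 28 as the end of Cycle 1 and of DLT assessment, so 28 days on drug naturally includes a scheduled omission.
- A reader might infer that SAP precedence cancels 9.3.1. Protocol Section 15 gives the SAP priority where the documents differ; silence is not a difference.
- A reader might infer that a toxic level has been cleared or the Part B dose undermined. The documents report no under-dosing rate, and Protocol 6.4.3 bases that dose on wider evidence: a DLT, cumulative hematologic toxicity, a Cycle 2 SAE, exposure and biomarkers.

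A further objection stands and shapes the remedy. If every DLT-free subject below 80% were dropped, those who lost doses to toxicity would go too, and their replacements could make a poorly tolerated level look cleaner.

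**Conclusion.** The gap is real and identical in both documents: followed as written, the definition gives an under-dosed, DLT-free completer full weight in the escalation decision. The consequence is a possibility, not a demonstrated bias. One such subject among the first three raises the chance of clearing a level from 0.43 to 0.49–0.54, an increase of 6 to 10 percentage points, if the DLT rate is 33% at full dosing and 10–20% when under-dosed. Neither those rates nor the frequency of under-dosing is in the documents, and the existing checks should keep it uncommon. The case for acting is that a primary-objective analysis set should not depend on an undefined, discretionary judgement when a numerical compliance limit is already in the protocol.

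**What to change.** Apply the following prospectively to the remaining Part A cohorts, with the same wording in SAP 2.3.2 and Protocol 8.5.2.

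- **Definition.** MTD-evaluable means having had a DLT in Cycle 1, whatever the dose taken, or having completed the 28-day window with at least 80% of the Cycle 1 doses planned for that schedule. The 80% is the lower limit already in Protocol 10.7 and SAP 8.3.
- **Counting.** Scheduled omissions are not missed doses. State how vomited doses count, because the formula in Protocol 10.7 is based on tablets taken.
- **Below 80%, unrelated to study-drug toxicity, no DLT.** Not evaluable for the MTD, replaced, and kept in the Safety Population.
- **Below 80% because of drug-related adverse events, no DLT.** Not dropped or replaced as mere non-compliers. Show them separately, with their compliance, to the safety review committee before the escalation decision.
- **The 40 subjects already enrolled.** List Cycle 1 compliance beside DLT status; do not reclassify them.
- **Denominator.** Reconcile the start of BID dosing (Day 2 in Protocol 8.4, Day 3 in Protocol 8.1 and SAP 3.1) so that the planned number of doses is defined.

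The cost is a short amendment to each document, one extra listing, and an occasional additional replacement subject. The compliance data are already collected.
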